8.1.4 Treatment Period (Weeks 0 to 52)

The 52-week Treatment Period (last dose Week 48) includes double-blind Induction Therapy over 12 weeks followed by OLE/double-blind LTE Therapy over 40 weeks. Subjects will continue in the study for 16 weeks after the last infusion associated with the subject's treatment period for on-site post-treatment assessments (refer to Figure 6.1-1 for overall study design). No other investigational or commercial agents or therapies other than KHK4083 and placebo and those described in Section 8.5 may be administered with the intent to treat the subject's UC.

8.1.4.1 Induction Therapy: Weeks 0 to 12 (Last Dose: Week 10)

Double-blind Induction Therapy (12 weeks) comprises Part A (Cohorts 1 - 3) for IV administration of multiple ascending doses of KHK4083 or placebo; and Part B (Cohort 4) for IV administration of the recommended dose of KHK4083 or placebo. Subjects in Part A are not allowed to participate in Part B of Induction Therapy. Select Sponsor personnel will be unblinded after the last subject completes Induction Therapy (refer to Section 8.4 for details).

Subjects in each cohort will be randomized in a 3:1 ratio to receive KHK4083 or placebo. Each subject in each cohort (Cohorts 1 - 4) will be administered one IV infusion of KHK4083 or placebo once every 2 weeks for a total of 6 treatments, i.e., Day 1 (Week 0), Day 15 (Week 2), Day 29 (Week 4), Day 43 (Week 6), Day 57 (Week 8), and Day 71 (Week 10).

- **Induction Therapy Part A (Cohorts 1 - 3):** 36 subjects (12 subjects/cohort) will be administered investigational product, i.e., 27 subjects (9 subjects/cohort) will receive KHK4083 and 9 subjects (3 subjects/cohort) will receive placebo once every 2 weeks (Weeks 0 to 10) as follows:

Cohort 1: 1.0 mg/kg or placebo

Cohort 2: 3.0 mg/kg or placebo

Cohort 3: 10 mg/kg or placebo

The cumulative safety data available after the first 8 of 12 subjects randomized in Cohort 1 will be evaluated by the Safety Monitoring Committee at Week 4 (~Day 29) to assess whether dosing will continue for subjects within Cohort 1 and if investigational product will be administered at the next higher dose level for subjects in Cohort 2. For Cohorts 2 and 3, the cumulative safety data available after the first 8 subjects in each cohort at Week 4 (~Day 29) and the first 4 subjects in each cohort at Week 6 (~Day 43) will be evaluated for continuation of all of the subjects and for dose escalation in the next cohort, i.e., Cohort 3 in Part A and Cohort 4 in Part B, respectively. The Safety Monitoring Committee and Sponsor may dose-reduce cohorts or not escalate to the planned doses based upon review of safety data (refer to Section 6.3).

- **Induction Therapy Part B (Cohort 4):** The recommended KHK4083 dose (one of three dose levels in Cohorts 1 - 3) is selected based on the safety data from Part A. At least 24 subjects will be administered the recommended dose of KHK4083 (18 subjects) or placebo (6 subjects) once every 2 weeks (Weeks 0 to 10) in Cohort 4.

For subjects in all cohorts, a sigmoidoscopy with biopsy will be performed at Week 12 to assess improvement in the mucosa based on a mean change in the mMES from Baseline (Week 0) to Week 12. It is highly recommended that the sigmoidoscopy with biopsy be performed within 7 to 13 days prior to the Week 12 visit.

8.1.4.2 Open-label/Long-term Extension Maintenance Therapy: Week 12 (First Dose) to Week 52

All subjects who qualify and continue double-blind LTE or start open-label maintenance therapy will be administered one KHK4083 or placebo (LTE) or one KHK4083 (OLE) IV infusion at Weeks 12, 16, 20, 24, 28, 32, 36, 40, 44, and 48 for a total of 10 additional treatments followed by an End-of-OLE/LTE Therapy visit at Week 52, and then proceed to the OLE/LTE Therapy Follow-up Period (Week 56 through Week 64). The treatment at Week 12 will be administered at the scheduled visit or within 7 days after Week 12. The OLE dose will be the same as the dose for that cohort during the induction therapy, unless dose-reduction is recommended by the Safety Monitoring Committee and Sponsor (see Section 6.3).

During OLE/LTE Therapy, corticosteroid (glucocorticoid) dosages of prednisolone or its equivalent will be permitted to be tapered (decreasing by up to 2.5 mg/day per week) and other concomitant medications for UC may be tapered. Bolus or “rescue” treatment with systemic corticosteroids or topical corticosteroid enemas or suppositories (in addition to the dose of oral corticosteroids at Screening) is permitted only after Week 12 evaluations are

complete. A sigmoidoscopy with biopsy will be performed at the End-of-OLE/LTE Therapy visit at Week 52 or within 21 days prior to Week 52.

8.1.5 Post-treatment Follow-up Period

Post-treatment Follow-up assessments will continue for 16 weeks after the last infusion associated with the subject's treatment period. For subjects who only receive Induction Therapy (i.e., last dose at Week 10 and do not continue in OLE/LTE Therapy), the Post-treatment Follow-up visits will be at Weeks 16, 20, and 26. For all subjects who receive both Induction Therapy and OLE/LTE Therapy (last dose at Week 48), the Post-treatment Follow-up visits will be at Weeks 56, 60, and 64. Subjects removed from the study for AEs will be followed until there is a return to the subject's baseline condition, or until a clinically satisfactory resolution is achieved. The date of the subject's last post-treatment study visit will be considered the End-of-Study date.

8.2 Method of Numbering Subjects and Assigning Subjects to Treatment Cohorts or Randomization

After a subject meets all study eligibility requirements at Screening (refer to Section 7.1 for enrollment procedures), the IRT system will be used by the Investigator (or designee) to randomize the subject to double-blind Induction Therapy on Day 1 (Week 0). Subjects randomly assigned in Cohorts 1 - 3 will receive either KHK4083 (one of three dose levels) or placebo in a 3:1 ratio during Part A of Induction Therapy. Additional subjects (Cohort 4) in a 3:1 ratio will receive the recommended KHK4083 dose or placebo during Part B of Induction Therapy. Subjects who received study medication in Part A are not allowed to participate in Part B.

At the end of Induction Therapy, subjects who meet all study eligibility requirements described in Section 7.4 will start receiving open-label KHK4083 at the same dose for that subject's cohort. Subjects who previously met all study eligibility requirements and entered the LTE will continue to receive KHK4083 or placebo during LTE Therapy phase; subject in the LTE may be eligible for the OLE up to Week 28 as described in Section 6.1.4.

8.3 Blinding During the Double-blind Treatment Period (Induction Therapy and Long-term Extension Therapy)

The subject and Investigator (or investigative site personnel) will not know the treatment to which the subject is randomized during the double-blind Treatment Period. Placebo will be administered by IV infusion to each cohort to ensure blinded treatment. The study is being

blinded to prevent bias in the safety evaluation, in particular the severity grading and causality determinations of AEs. However, at any time during the study, if a medical emergency occurs and subject treatment must be known, the blind may be broken according to the procedure in Section 8.4.

An assigned pharmacist (or qualified designee) at each investigative site will be unblinded and responsible for preparing the appropriate treatment based on the treatment assignment by the IRT system. The unblinded pharmacist (or qualified designee) will ensure that the investigational product administered to each subject is labeled such that the treatment identity cannot be determined.

8.4 Unblinding During the Treatment Period and After Induction Therapy and Long-term Extension Therapy

A subject's treatment assignment should only be unblinded by the Investigators and/or Sponsor's Medical Monitor when knowledge of the treatment is essential for the further management of the subject or may impact the safety of subjects in current and/or subsequent cohorts. Unblinding for any other reason will be considered a protocol violation.

The Investigators are strongly encouraged to contact the Medical Monitor before unblinding any subject's treatment assignment. However, the Investigator may unblind for safety reasons without prior notification, but must contact the Medical Monitor within one business day after the event and must document the unblinding in the subject's source records together with a completed SAE form. Any instance of unblinding will be reported in the clinical study report.

The Investigator or the designee who breaks the blind must record the date and the reasons as appropriate. In such cases, treatment with the investigational product must be stopped and the Sponsor must be contacted immediately to determine whether the subject should be withdrawn from the study. Every attempt should be made to contact the Sponsor before the blind is broken.

The study will be unblinded to select personnel from the Sponsor (or consultants acting on behalf of KKD) and/or from participating Contract Research Organizations. The individuals will be identified in the Blinding Plan and Unblinding Processes for Study 4083-002. The study will be blinded to all other study personnel/consultants, investigative site personnel, and study subjects.

After the last subject completes Part B of Induction Therapy, the study will be unblinded to additional select Sponsor personnel. The study will be unblinded to all study

personnel/consultants following database lock after the last subject completes the last follow-up visit.

8.5 Prior and Concurrent Therapy

All medications (including prescription, non-prescription and supplements) for treatment of UC taken within 6 months prior to Screening; any other medication taken 1 month prior to Screening; and any concomitant medications (including tracking probiotic usage) during the study will be collected. For all biologic treatments, the reason for discontinuation should be collected at Screening. Combination medications should be recorded by trade name.

Stable doses of the following concomitant medications are permitted for UC treatment during the study as specified below:

- Aminosalicylates (5-ASA or mesalamine ≤ 4.8 g/day; sulfasalazine ≤ 3 g/day) for at least 14 days prior to the Screening visit; and/or
- Oral glucocorticoids, ≤ 20 mg/day prednisolone or the equivalent, or budesonide ≤ 9 mg/d for at least 14 days prior to the Screening visit (or for 4 weeks if a course of corticosteroids had started at less than 8 weeks prior to Screening visit); and/or
- Azathioprine up to 3 mg/kg/day or 6-mercaptopurine up to 1.5 mg/kg/day for a total treatment period of at least 12 weeks, including 4 weeks of stable treatment, prior to the Screening visit.

Supportive therapy to manage symptoms or AEs is acceptable. Daily, chronic antidiarrheals should not be taken.

One bolus or “rescue” treatment for up to 7 days with each of the following: systemic corticosteroids or topical corticosteroid enemas or suppositories (in addition to the dose of oral corticosteroids at Screening) is permitted only after Week 12 evaluations are complete. Topical anti-inflammatory agents may be permitted only after Week 12 evaluations are complete and application must be withheld for at least 2 weeks prior to the sigmoidoscopy at Week 52/End-of-Treatment visit.

Dose reductions of concurrent medications are permitted for AEs from Baseline through the end of the study as allowed by the protocol. Other dose adjustments of concurrent medications (including corticosteroids and other treatments for UC) are permitted after the Week 12 visit (per Investigator’s judgment), i.e., during OLE/LTE Therapy and the Induction Therapy and OLE/LTE Therapy Follow-up Periods. After the Week 12 visit, corticosteroid (glucocorticoid) dosages of prednisolone or its equivalent may be tapered by approximately 2.5 mg/day per week, at the Investigator’s discretion. Subjects who have recurrence of clinical symptoms may increase their chronic (> 7 days) dose of corticosteroids and other

treatments for UC may increase up to 110% of the original dose at the start of Induction Therapy.

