7.3 Analysis of exploratory efficacy endpoints

All exploratory efficacy variables will be summarized by treatments. The changes from Baseline in mMES, UCEIS and total Mayo Clinic score as well as Baseline and Week 52 will be summarized by treatments. In addition, the partial Mayo Clinic scores (without sigmoidoscopy) and changes from Baseline will be summarized by study visit at Weeks 16, 20, 24, 28, 32, 36, 40, 44, 48, and 52 and at OLE/LTE Therapy Follow-up Period visits (Weeks 56, 60, and 64).

The change from Baseline in HRQL based on IBDQ will be analyzed for total score and 4 subscale scores at all study visits (Weeks 2 to 52, including Induction Therapy Follow-up Period visits (Weeks 16, 20, and 26) and OLE/LTE Therapy Follow-up Period visits (Weeks 56, 60, and 64).

Remission (mMES of 0 or 1, stool frequency subscore of 0 or 1 and rectal bleeding subscore of 0) rates at Week 12 will be summarized. Remission rates at Week 52 will be summarized by Double-Blind Period and OLE Therapy Period as well.

Clinical response and clinical remission will be summarized at Week 52. The percentage of subjects with mucosal healing, and the percentages of subjects with improvement in the mucosa (change from Baseline of at least a 1-point improvement in the mMES and/or in the modified Baron endoscopic scores) at Week 52 will be summarized by Double-Blind Period and OLE Therapy Period.

Durable clinical response and durable clinical remission at Week 52 will be summarized by Double-Blind Period and OLE Therapy Period. Durable clinical response and durable clinical remission at Week 52 will be defined as follows:

- Duration clinical response at Week 52 will be defined in the case that clinical response is present at both Weeks 12 and 52.
- Duration clinical remission at Week 52 will be defined in the case that clinical remission is present at both Weeks 12 and 52.

Glucocorticoid-free clinical remission at Week 52 will be summarized by Double-Blind Period and OLE Therapy Period. At Weeks 16 through 52 and through the OLE/LTE Therapy Follow-up Period (Week 56 through Week 64), the change from baseline in corticosteroid (glucocorticoid) dosages and the duration of glucocorticoid-free treatment will be summarized. Those parameters definitions are shown below.

- Glucocorticoid-free clinical remission at Week 52

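### Most Week 52 binary endpoints can be met under recent systemic steroid rescue or a raised steroid dose, because they are defined by scores alone and no withholding or non-response rule covers that use

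*Protocol*

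**What the plan says.** **Which section governs.** Protocol 8.1.4 limits treatment of UC to the study products and what Section 8.5 describes. Section 8.5.1 likewise bars other UC therapy during the OLE and LTE unless it is specified there.

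**What 8.5 allows after the Week 12 evaluations.**
- One rescue "treatment for up to 7 days with each of the following: systemic corticosteroids or topical corticosteroid enemas or suppositories", on top of the oral steroid dose at Screening.
- Topical anti-inflammatory agents, on the condition that "application must be withheld for at least 2 weeks prior to the sigmoidoscopy at Week 52/End-of-Treatment visit".
- Dose changes at the investigator's discretion: "Other dose adjustments of concurrent medications (including corticosteroids and other treatments for UC) are permitted after the Week 12 visit".
- A longer steroid increase on relapse, of more than 7 days, in a sentence that also takes in other UC drugs and sets a limit: "treatments for UC may increase up to 110% of the original dose at the start of Induction Therapy".

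**What 8.1.4.2 says.** It permits bolus or rescue "treatment with systemic corticosteroids or topical corticosteroid enemas or suppositories" after Week 12 and does not repeat the limit on number or length.

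**Consequence for treatment.** Protocol 7.5.3 stops investigational product when a prohibited medication is needed.

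**Week 52 endpoints.** SAP 3.4.3 and Protocol 10.3 define them from Mayo components and endoscopic scores, and SAP 7.3 states: "Clinical response and clinical remission will be summarized at Week 52". The exception is glucocorticoid-free clinical remission, which requires that no listed glucocorticoid be used from Week 16 through Week 52. SAP 9.3 lists only medications started from Day 1 with ATC code H02AB. The missing-data sections (Protocol 12.6, SAP 4.4) are silent on rescue.

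**The concern.** Systemic steroid given shortly before Week 52 can lower stool frequency, bleeding, the global assessment and the endoscopic score. The protocol accepts this for topical agents by requiring a washout before the sigmoidoscopy, but states none for systemic steroid or for a raised oral dose. The SAP has no rule that treats such use as non-response. A Week 52 rate can therefore include subjects whose scores partly reflect steroid rather than KHK4083 (or LTE placebo), and the planned tables would not show how many.

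Unclear wording in 8.5 adds to this. It leaves open how much steroid a subject may receive before the use becomes prohibited under 7.5.3.

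**Working it through.** The plan gives no figure for rescue, so there is none to reproduce. Its one planning figure, 51/0.85 = 60 randomized, does not enter. The check compares windows and definitions.

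**1. Diary window.** Protocol 9.3 takes the Week 52 diary items from the 7 days before the visit, using the 2 to 3 qualifying days closest to it. A 7-day systemic course ending the day before the visit covers days −7 to −1, which is 7 of 7 days. Every usable diary day can be an on-steroid day.

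**2. Sigmoidoscopy window.** The procedure may be done at the visit or up to 21 days before (8.1.4.2).
- Done at the visit, it follows the course in step 1 by one day.
- Done between day −21 and day −8, it precedes that course, so the course cannot affect the endoscopic score. An earlier 7-day course, or a longer dose increase, still could.

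**3. Topical rule.** The 2 weeks run back from the sigmoidoscopy, not from the visit. With a sigmoidoscopy on day −21, topical treatment could resume afterwards and cover days −7 to −1. The rule protects the endoscopic score but not the diary items.

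**4. What glucocorticoid-free remission leaves out.**
- It looks from Week 16, while rescue opens after Week 12. That omits 4 of the 40 extension weeks, 4/40 = 10%. SAP 7.3 puts steroid from those weeks into its baseline count (Day 1 to the day before Week 16).
- Steroid started before Day 1 is outside the SAP 9.3 list. Whether a later increase of such a drug counts depends on whether it is recorded as a new medication, which the documents do not say.
- Products coded other than H02AB are not counted.
- The SAP's steroid dosage variable is a number of administrations, so a higher dose at the same frequency leaves it unchanged.

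**5. Unclear points within 8.5.**
- *Each* followed by *or* does not settle whether both routes may be used.
- The dose-adjustment sentence has no ceiling.
- The 110% limit may cover steroids or only other UC treatments. If it covers steroids, the largest permitted entry dose of 20 mg/day prednisolone gives 1.10 × 20 = 22 mg/day. If it does not, no ceiling is stated for the chronic steroid dose.

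**6. Size, as illustration only.** Let r be the share of subjects with steroid use in the look-back and q the share of those who meet the score criteria. Counting them as non-response lowers the rate by r × q. Both values are assumed:

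| r | q = 25% | q = 50% | q = 75% |
|---|---|---|---|
| 10% | 2.5 points | 5 | 7.5 |
| 20% | 5 | 10 | 15 |
| 40% | 10 | 20 | 30 |

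If all 27 subjects planned for the recommended dose reached Week 52, this is 27 × 0.025 = 0.7 to 27 × 0.30 = 8.1 subjects.

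**7. Direction between arms (LTE only).** Assume rescue in 10% on active and 30% on placebo, a 30% response in unrescued subjects of both arms, and 75% in rescued subjects.
- As scored: (0.9 × 0.30 + 0.1 × 0.75) − (0.7 × 0.30 + 0.3 × 0.75) = 0.345 − 0.435 = −0.09.
- Rescue as non-response: 0.27 − 0.21 = +0.06.

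Scoring without regard to rescue need not favour the drug.

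**The case against.** The strongest reply is that this is a descriptive extension. All Week 52 endpoints are exploratory, SAP 4.1 says that no hypothesis testing will be carried out, and SAP 4.5 bases the proof-of-concept judgement on Week 12 data, collected while rescue is barred. The OLE has no concurrent control, and scoring regardless of rescue is a legitimate choice. This stands as a limit on importance. It does not supply the missing statement of how rescue is handled, and it does not let a reader see how far the rates depend on it.

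The SAP also does not ignore steroids. It plans counts and steroid-free duration by track (Tables 14.2-3.5.1 to 14.2-3.5.4), concomitant medications by extension period (Tables 14.1-3.3 and 14.1-3.4) and a subject listing (16.2.6-3.2). This stands too. What is missing is a rescue flag and a link to response.

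Stronger readings that a reader might infer, but that the documents do not support:
- *Rescued subjects are counted as responders.* They count only if they meet the score criteria. The gap is that nothing prevents this.
- *Section 8.1.4.2 grants unlimited rescue, so retention to Week 52 depends on which section a site reads.* Section 8.1.4 refers to 8.5, so 8.1.4.2 is better read as a shorter restatement that omits the limit. The ambiguity that matters is inside 8.5.
- *The share of subjects affected can be worked out from a flare model.* No flare or rescue rate is given, and a comparison with unlimited rescue lacks support in the text.

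**Conclusion.** The point holds in a limited form. Except for glucocorticoid-free clinical remission, the Week 52 binary endpoints can be met by a subject with recent systemic rescue or a raised steroid dose. Glucocorticoid-free remission does not close the gap for the others, and its own steroid definition is incomplete.

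The size is unknown. The 2.5 to 30 points above follow from assumed values of r and q and are not an estimate. A reader should not extend the point to the Week 12 primary and secondary endpoints, or to the Week 12 part of durable response and remission, because rescue opens only after those evaluations.

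Separately, the statements in 8.5, and their restatement in 8.1.4.2, must be reconciled. No view is taken here on which clinical rule is right.

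**What to change.** **SAP 7.3.** Keep the score-based endpoints and add a supplementary version of each Week 52 binary endpoint. In it, count as non-response any subject who used rescue steroid, or steroid or other UC therapy above the induction-start dose, within a pre-specified look-back. The look-back must cover both the sigmoidoscopy, up to 21 days before the visit, and the 7-day diary window. One example is from 4 weeks before the sigmoidoscopy through the visit. Identify this use from all concomitant-medication records, not only the SAP 9.3 list.

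**Steroid tables.** Flag rescue separately in the tables already planned, by treatment and track.

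**Protocol.** The sponsor should reconcile the statements in 8.5 with one another and with 8.1.4.2, and state which uses count as prohibited under 7.5.3.

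**Cost.** A protocol clarification, some SAP wording and a little more programming. Concomitant medications are already collected. The dose comparison assumes that dose is recorded on the medication page, which the documents do not show. The supplementary Week 52 rates may be slightly lower.

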8.5.1 Prohibited Treatment

During Screening and Induction Therapy, subjects are not permitted to receive rescue therapy for UC including increases in corticosteroids or other medications for UC treatment, except as specified above (Section 8.5).

During Screening, Induction Therapy, and OLE/LTE Therapy, subjects are not permitted to receive any additional experimental therapy or any other therapy to treat the UC, except as specified above. The following is a list of specific prohibited treatments:

- B-cell depleting agents including vedolizumab, natalizumab, efalizumab or rituximab or other lymphocyte-depleting treatments, including but not limited to alkylating agents (such as cyclophosphamide or chlorambucil) and total lymphoid irradiation;
- Methotrexate, cyclosporine, mycophenolate, tacrolimus, thalidomide, or other immune altering drugs; (*Note: ophthalmologic preparations are permitted.*)
- TNF antagonists.

The above prohibited treatments are permitted during the Induction Therapy Follow-up Period and OLE/LTE Therapy Follow-up Period of the study.

Some medications, such as nonsteroidal anti-inflammatory drugs, may need to be administered or held prior to a sigmoidoscopy with biopsy. Those will be detailed in a sigmoidoscopy manual.

